12.6.3.3 Format of the SUSARs reports

Electronic reporting is the expected method for expedited reporting of SUSARs to the competent authority. The format and content, as defined by the competent authority, should be adhered to.

13. Pregnancy Reporting

Pregnancies in participants will not be recorded or reported in this trial unless they meet the criteria of SAR, in which case the SAR reporting form will need to be completed.

14. Evaluation of Results (Definitions and Response/Evaluation of Outcome Measures)

All data will be presented to the TSC, who will meet regularly throughout the trial and who will provide overall supervision of the trial.

14.1 Response criteria

14.1.1 Mortality

This will be measured from the date of randomisation up to the 12-month follow-up and will be reported for all deaths due to all causes. The cause of death is to be recorded if known.

14.1.2 Quality of life and disability

Quality of life will be assessed by employing the EQ-5D-5L questionnaire to generate quality-adjusted life years.

The GOS-E outcome instrument will be used to assess disability and recovery.

14.1.3 Assessment of DVT or PE occurrence

Symptomatic DVT or PE will be investigated as per standard clinical practice either by compression Doppler ultrasound of the femoral and popliteal veins or CTPA, as appropriate.

14.1.4. Progression of intracranial haemorrhage

This will be detected via routinely performed imaging

15.1 Statistical methods

The principal statistical analysis will be performed on an intention-to-treat basis and will include all randomised patients, regardless of subsequent treatment compliance.

Primary analysis

Our primary outcome will be VTE within 30 days of TBI. A survival analysis approach will be used to model the time to VTE and account for censorings before 30 days due to dropout. A Cox proportional hazards model will adjust for baseline covariates, including the randomisation strata (presence of extra-cranial injury and initial admission to ward vs critical care), with further details finalised in the statistical analysis plan. The difference in absolute VTE rates at 30 days will be the primary estimate, as opposed to a hazard ratio. The g-formula approach will be used to estimate the absolute difference standardised across the study population of baseline covariates, with bootstrapping used to provide a confidence interval and p-value. Using VTE rates at 30 days as the primary outcome standardises this study with existing literature on VTE rates quoted by NICE.

Secondary analysis

Further secondary endpoints will be summarised using appropriate techniques according to whether the variable is binary, categorical, continuous or time-to-event. Categorical and binary variables will be summarised using bar charts, frequency tables and logistic regression comparisons. The GOSE will be analysed with an ordinal method adjusting for baseline covariates. Continuous variables will be summarised, broken down by treatment arm, using Box plots, mean, median, SD, max, min and compared using linear regression. Time-to-event variables will be summarised using Kaplan-Meier plots and compared using the log-rank test or Cox proportional hazards model.

The selected secondary endpoints reflect all the outcomes highlighted by the original NIHR commissioning brief. The GOSE can reveal the impact of TBI on the level of consciousness, activities of daily living, functional independence, work and quality of life (31) and will be used to assess longer-term functional outcomes for study participants. Further secondary endpoints will be summarised using appropriate techniques according to whether the variable is binary, categorical, continuous or time-to-event. Categorical and binary variables will be summarised using bar charts, frequency tables and logistic regression comparisons. Continuous variables will be summarised, broken down by treatment arm, using Box plots, mean, median, SD, max, min and compared using linear regression. Time-to-event variables will be summarised using Kaplan-Meier plots and compared using the log-rank test.

Subgroup analysis

We will explore subgroups focussing on those factors most relevant to the research question, which are TBI severity and type, extracranial injuries and body mass index. The study statistician will prepare a detailed statistical analysis plan.

Convolutional neural network (CNN) CT scan analysis

All CTs obtained for subjects during routine care will be uploaded onto a secure image repository. Images will be pseudo-anonymised and defaced. Lesion progression on CT will be assessed using a convolutional neural network capable of multiclass segmentation, which has already been developed and validated on a broad range of clinical sites and scanners as part of CENTER-TBI, a prospective European TBI cohort study (38).

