9.3.4. Randomisation

A secure web-based randomisation service (Sealed Envelope) will be used for the randomisation of eligible patients. Suitably trained staff will access the secure website and enter the necessary information. The system will provide an immediate allocation along with the patient identifier number for the trial. A confirmatory email will be sent to the email addresses of the study team members at the site randomising the patient. Trial investigators (or delegates) from the central team will be available 24-hours in case of problems or queries with the randomisation system. The presence of extracranial injury and initial admission to the ward vs critical care will stratify allocation. Stratified block randomisation will be used.

Early PTP arm - defined as administration of PTP within 72 hours of TBI

Late PTP arm - defined as administration of PTP after a minimum of 120 hours from TBI or PTP not administered at clinical discretion. PTP should not be administered within 120 hours and administration will be recorded as protocol deviation

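### Section 15.1 gives two conflicting methods for the secondary time-to-event outcomes, and neither carries the randomisation factors into the secondary log-rank, logistic or linear comparisons

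*Protocol*

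**What the plan says.** **Randomisation (Protocol 9.3.4).** Stratified blocks are used: "The presence of extracranial injury and initial admission to the ward vs critical care will stratify allocation".

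**Primary analysis (15.1).** "A Cox proportional hazards model will adjust for baseline covariates, including the randomisation strata".

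**Secondary analysis, first version (15.1).** "The GOSE will be analysed with an ordinal method adjusting for baseline covariates". Time-to-event outcomes are "compared using the log-rank test or Cox proportional hazards model". Binary and categorical outcomes get "frequency tables and logistic regression comparisons", and continuous outcomes get linear regression. No covariates are named for any of these except GOSE.

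**Secondary analysis, second version (15.1, the paragraph that starts from the commissioning brief).** Nearly the same sentences return: "Categorical and binary variables will be summarised using bar charts, frequency tables and logistic regression comparisons", and continuous outcomes are summarised "using Box plots, mean, median, SD, max, min and compared using linear regression". The GOSE method sentence is gone, and the time-to-event sentence now ends at the log-rank test: "Time-to-event variables will be summarised using Kaplan-Meier plots and compared using the log-rank test".

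Section 15.1 leaves further details of the primary model to the statistical analysis plan, and its subgroup paragraph announces a detailed plan. That plan is not among the documents reviewed.

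**The concern.** There are two linked problems.

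1. The two versions disagree on whether a Cox model may be used for secondary time-to-event outcomes. Someone drafting the analysis plan cannot tell which one governs.
2. Where the authors wanted adjustment they said so, for the primary outcome and for GOSE. The remaining comparisons are named bare. A log-rank test takes no covariates, so unless it is declared stratified it ignores the strata.

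Stratified allocation removes most of the between-stratum variation from the treatment comparison. A log-rank test that ignores the strata still counts that variation in its variance, so it rejects too rarely when the strata predict outcome. All-cause mortality and haemorrhage progression are named comparisons in section 8.5.2, and for a harm outcome a conservative test errs towards missing a difference.

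**Working it through.** **The plan's own figures.** Section 15.3 gives power for the primary outcome only. Its base case (10% vs 5%, two-sided 5%, 90% power, pooled variance, 1:1) reproduces at 1164. No rate, effect or power is stated for mortality or any other secondary outcome, so there is no secondary figure to reproduce, and nothing in 15.3 depends on this point.

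**The texts side by side.**

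| Outcome type | 15.1, first version | 15.1, second version | Randomisation factors named? |
|---|---|---|---|
| Primary VTE | Cox | not repeated | Yes |
| GOSE | ordinal, adjusted for baseline covariates | method not repeated | Covariates yes; strata not named |
| Binary/categorical | logistic | logistic | No |
| Continuous | linear | linear | No |
| Time-to-event | log-rank or Cox | log-rank only | No |

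**Size of the test under assumed mortality.** Assume half the patients are on wards and half in critical care, with arms balanced within each. With follow-up fixed at 12 months, the log-rank test behaves roughly like a comparison of proportions. The unstratified variance is proportional to p(1−p) at the pooled rate p; the actual variance is proportional to the mean of the within-stratum terms. True type I error is then about P(|Z| > 1.96/√ratio), where ratio = within/pooled.

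- 5% vs 15%: pooled 0.10×0.90 = 0.0900; within (0.0475+0.1275)/2 = 0.0875; ratio 0.972; cut-off 1.988; type I error 4.7%.
- 5% vs 30%: pooled 0.175×0.825 = 0.1444; within (0.0475+0.21)/2 = 0.1288; ratio 0.892; cut-off 2.076; type I error 3.8%.
- 5% vs 40%: pooled 0.225×0.775 = 0.1744; within (0.0475+0.24)/2 = 0.1438; ratio 0.824; cut-off 2.159; type I error 3.1%.
- 3% vs 50%: pooled 0.265×0.735 = 0.1948; within (0.0291+0.25)/2 = 0.1396; ratio 0.716; cut-off 2.316; type I error 2.1%.

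**Simulation of the same settings** (756 per arm, exponential survival, 3000 trials each). At 5% vs 30-40% the unstratified log-rank rejects 3.6-4.0% of true nulls; a repeat with 6000 trials gave 3.2-3.7%, the same within simulation error. Power for HR 0.70 is 72-83% unstratified and 76-87% stratified. For HR 0.70 or, in the direction of harm, HR 1.4, the loss is 3-5 points. At 5% vs 15% it is only about 1-2 points. At 3% vs 50% type I error is 1.9% and power is 86% vs 92%.

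These are strong assumptions. Since HR = ln(1−critical-care rate)/ln(1−ward rate), 5% vs 30% is 0.357/0.0513 ≈ 7.0 and 5% vs 40% is 0.511/0.0513 ≈ 10.

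**Simulation over a wider range** (N = 1512, two binary factors at 50% each, four strata, 4000 trials per cell, Monte Carlo error about 0.7 points on power; treatment HR 0.60, 0.72 and 0.77 at the three mortality levels). The entries are power gained by stratifying the log-rank test.

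| HRs of the two factors | 10% mortality | 20% | 30% |
|---|---|---|---|
| 1 and 1 | 0.0 | −0.2 | −0.3 |
| 1.5 and 2 | +0.4 | +1.4 | +1.4 |
| 2 and 3 | +0.7 | +2.3 | +4.1 |
| 2 and 5 | +1.2 | +4.7 | +8.4 |

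The largest cell is 67.5% rising to 75.8%. Null rejection was 3.1-5.2% unstratified and 4.4-5.4% stratified.

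**Logistic regression**, same design with odds ratios for the factors: adjustment gains 0.5-0.8 points (1.5 and 2), 1.0-2.1 (2 and 3) and 1.4-4.0 (2 and 5). The mechanism differs here: against the adjusted model, leaving out the strata pulls the odds ratio towards 1 rather than enlarging its standard error.

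**The case against.** The strongest reply is that covariate lists for secondary models, and whether a log-rank test is stratified, commonly belong in the analysis plan, which is not shown. The protocol never uses the words unstratified or unadjusted; logistic and linear models can carry the strata; and the first version already permits a Cox model. This stands in large part. It means that one cannot say the regressions will be unadjusted. It does not remove the contradiction between the two versions, because there the protocol names the test twice and differently.

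A reader might also infer that the strata are strong prognostic factors and that the trial loses material power on mortality. The documents do not support that. They state no association between either factor and mortality or haemorrhage progression; section 6.3 links major extracranial injury only to receiving prophylaxis. Nor do they assign mortality to the log-rank test: section 8.6.2 lists it at 7 days, 30 days and 12 months, which could equally be analysed by logistic regression, where the loss is smaller. The same applies to haemorrhage progression.

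Finally, any error is conservative, and no secondary outcome is powered, so no stated figure becomes wrong. Both points stand and keep this minor.

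**Conclusion.** The point holds in a limited form. The inconsistency within section 15.1 is certain. The absence of the randomisation factors from the secondary log-rank, logistic and linear comparisons is a fact of the text; that they will actually be left out is an inference from silence.

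If they are left out, the cost depends on mortality rates and prognostic strength that the protocol does not give: from nothing with no prognostic effect, through the 3 to 5 points found at 5% vs 30-40% mortality, to 8 points in the most extreme cell examined. All of this assumes evenly sized strata and balanced arms. False positives do not increase. Where the strata carry no information, stratifying costs at most 0.3 points, which is within simulation error, so there is no real trade-off. This is a minor, free improvement.

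**What to change.** In section 15.1:

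1. Delete the repeated secondary-analysis sentences in the second version, keeping the rationale for choosing the secondary endpoints and GOSE.
2. State once that secondary time-to-event comparisons use a log-rank test stratified by extracranial injury and ward versus critical care, or a Cox model adjusted for them.
3. State that the secondary logistic and linear models include the same two factors.

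The cost is wording only. Both factors are needed to randomise, and section 15.5 says that the relevant covariates must be recorded before randomisation, so no new data are required. The sample size and the primary analysis do not change.

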15.2 Interim analysis

An interim analysis may be performed after an appropriate number of participants (to be decided by TSC) have observed 30 days follow-up, shortly before recruitment is scheduled to be halted, to confirm the sample size. The TSC and statistical team will agree jointly on the most appropriate timing of this interim analysis, considering the case mix and parameters the TSC wishes to estimate. If the sample size needs to be revised, we can incorporate the uncertainty in absolute VTE rates to achieve an acceptable conditional power as determined by the TSC. The interim analysis will be outlined in the TSC Charter.

15.3 Number of participants to be enrolled

The number of participants to be enrolled is 1512 patients. The rationale for this sample size is as follows. The literature shows that a 5% decrease in clinically important VTE rate is deemed a plausible and clinically important treatment effect (39–41). 1164 patients are required to have a 90% chance of detecting, as significant at the 5% level, a decrease in the primary outcome measure from 10% in the "late" group (16, 17, 42) to 5% in the "early" group. However, should the assumed rate in the "late" group be an underestimate, then power will be lost. A comparison of 12% vs 7%, would need 1441 patients. Should the treatment effect be slightly smaller, e.g. a 4.6% reduction equivalent to a comparison of 10% vs 5.4%, then the power of 90% would be maintained with 1441 patients. Hence, adjusting for a loss to follow-up of up to 5%, a robust total sample size of 1512 will be recruited.

The rationale for a 5% loss to follow-up rate is that patients who suffer brain injury often have persistent cognitive difficulties, thus creating challenges with follow-up assessments. However, this 5% is a conservative estimate, and our previous trials drop-rate ranged from 1-3% (43). In recent neurotrauma trials delivered by Cambridge CTU, loss to follow-up was < 4% at 6 months (2.3% for the RESCUEicp RCT, 3.3% for the Dex-CSDH RCT and 3.7% for RESCUE-ASDH RTC). Given that this trial's primary endpoint is 30 days, which is much shorter than 6 months, we are confident that loss to follow-up will be minimal. However, we will monitor this closely during the pilot and substantive phases to ensure it does not exceed.

15.4 Criteria for the premature termination of the trial

There are no defined criteria for the premature discontinuation of the trial. Following the pilot phase, the trial will progress into the substantive study provided certain criteria based on recruitment are met (see section 8.3). However, the TSC will make recommendations on discontinuing the trial following a review of the ongoing data presented at regularly scheduled meetings.

15.5 Procedure to account for missing or spurious data

For the primary analysis, missing data will be assumed to be missing at random. A sensitivity analysis will be carried out by performing a complete case analysis. As the relevant covariates must be recorded before the participant can be randomised, we aim to have minimal missing baseline data. There is also an excellent track record for UK-led neurosurgical studies in achieving extremely high rates for follow-up (STICH, STICH II and RESCUE studies).

15.6 Economic evaluation

An economic analysis will be undertaken to compare the cost-effectiveness of early PTP versus late PTP, and a 12-month trial economic evaluation will be conducted. Costs will be estimated from the viewpoint of the NHS and include LMWH, hospital admissions, potentially related medication use, investigations, readmissions and outpatient appointments using data from HES. The main outcome

measure will be the EQ-5D-5L (44) at day 30/discharge, 6 and 12-month follow-up, enabling Quality Adjusted Life Year (QALY) scores to be estimated. Based on a pre-specified Health Economic Analysis Plan (HEAP), the analysis will be undertaken to estimate the incremental cost and incremental effect (QALY gain) associated with early PTP compared to late PTP. Assuming dominance does not occur (where one option is estimated to be more effective and less costly than the other option), the incremental cost-effectiveness ratio (ICER) of early PTP will be estimated and assessed concerning a range of cost-effectiveness thresholds e.g., £20,000-£30,000 per QALY has been recommended by NICE. The associated level of uncertainty will also be characterised by estimating the cost-effectiveness acceptability curve / conducting sensitivity analysis. This methodological approach has been adopted in a previous trial of TBI patients (37) and will enable recommendations as to the cost-effectiveness of early PTP to be made.

15.7 Definition of the end of the trial

The end of the main trial will be the date of the last participant's final assessment/loss to follow-up.

16. Data handling and record keeping

16.1 eCRF

Electronic case report forms (eCRFs) will be used to collect the data. All data will be entered into a secure electronic database. The database, which will be MHRA and GDPR-compliant, will be secured by appropriate access control and password protection.

All trial data will be transferred into the CRF which will be de-identified. All trial data in the CRF must be extracted from and be consistent with the relevant source documents. The investigator or designee must complete, date and sign the CRFs in a timely manner. It remains the responsibility of the investigator for the timing, completeness and accuracy of the CRF pages. The CRF will be accessible to trial coordinators, data managers, investigators, Clinical Trial Monitors, Auditors and Inspectors as required.

Participating sites will be provided with eCRF completion guidelines and given training on data entry.

The central coordinating team will check the data entered into the trial database for errors, inconsistencies and omissions. If missing or questionable data are identified, the central coordinating team will request that the data be clarified.

16.2 Use of Personal Identifiable Data

Trial participants will provide explicit consent to the use of identifiable data for the purposes of the conduct of the trial. The TOP-TBI trial management team will hold Personal identifiable data (PID) on all participants, including name, date of birth, gender, NHS number or equivalent, home address and postcode, telephone number and email address where applicable. Personal identifiable data (PID) will be accessible to limited members of the TOP-TBI trial team within the Cambridge Clinical Trials Unit; the sponsor monitors auditors and inspectors as required. It is necessary to 1) perform linkage to national datasets: NHS England, Secure Anonymised Information Linkage (SAIL) databank, Public Health Wales, electronic Data Research and Innovation Service (eDRIS), Public Health Scotland and Belfast Health and Social Care Trust, and 2) to contact participants for follow-up assessments and is therefore imperative to the conduct of the trial.

All PIDs downloaded from NHS England and the equivalent national health record organisations will be stored securely on the University of Cambridge, School of Clinical Medicine Secure Research Computing Platform (SRCP). The SRCP is registered and approved under the NHS Digital Data Security and Protection Toolkit and is ISO 27001 certified.

16.2 Source data

To enable peer review, monitoring, audit and/or inspection, the investigator must agree to keep records of all participating participants (sufficient information to link records e.g., hospital records) and all original signed informed consent forms. The electronic CRFs should also be readily available.

In this trial, the following documentation will be considered as source data:

- Patient medical notes, electronic and/or paper as applicable
- Radiology Reports
- Screening Logs
- Informed Consent Forms
- Questionnaires
- Source data worksheets will be provided to sites as required to assist them in documenting medical history, concomitant medications, and AESI.

16.3 Data protection & participant confidentiality

All investigators and trial site staff involved in this trial must comply with the requirements of GDPR, the Data Protection Act 2018 and the Trust Policy regarding the collection, storage, processing, transfer and disclosure of personal information and will uphold the Act's core principles.

17. Trial steering committee

As this trial is a low-risk Type A and involves licensed IMPs with well-documented safety characteristics, the trial will only have a Trial Steering Committee (TSC) that can also review SARs/SUSARs. The TSC will provide overall supervision with respect to the conduct of the trial as well as oversee the ethical and safety aspects of the trial and will advise the TMG. Full details of the TSC membership and remit can be found in the TSC charter.

18. Ethical and regulatory considerations

18.1 Ethical committee review

Before the start of the trial or implementation of any amendment, we will obtain approval of the trial protocol, protocol amendments, informed consent forms and other relevant documents, if applicable, from the REC. All correspondence with the REC will be retained in the Trial Master File/Investigator Site File.

Annual reports (DSURs) will be submitted to the REC in accordance with national requirements. It is the Chief Investigator's responsibility to produce the annual reports as required.

